NCT02536846

Protocol Title: The effects of antipsychotic drugs on brain metabolism in healthy individuals

Protocol Version date: 4/5/21

PRINCIPAL INVESTIGATOR

[name], MD, PhD

[contact]

Schizophrenia & Bipolar Disorder Program

e-mail: [contact]

PROTOCOL TITLE

The effects of antipsychotic drugs on brain metabolism in healthy individuals.

BACKGROUND

Schizophrenia is a complex psychiatric disorder characterized by alterations in brain structure. It remains unclear yet whether some of these alterations may be related to pathophysiology of illness per se, or are the consequence of brain exposure to the effects of psychotropic drugs. In recent years evidence suggests that exposure to the effects of psychotropic drugs may contribute to some structural and other changes in brain. In this study, we aim to evaluate the effects of short-term antipsychotic medication use in healthy subjects on neuroimaging markers. We will also examine effects of antipsychotic exposure on neurocognitive performance.

The primary aim of this study is to investigate antipsychotic drug effects on brain energy metabolism in 30 healthy people by administering olanzapine over 15 days and using 31P MRS imaging at 4 Tesla. Secondary aims include studying the effects of olanzapine on other neuroimaging markers collected using MRI approaches and cognition.

We plan to study the levels of chemicals associated with cellular energy metabolism: kinetics of enzymes involved in cellular energy metabolism in brains of healthy people before and after use of antipsychotic drug olanzapine for 15 days. In addition, we will also collect data on the structure of the gray matter and white matter; resting state functional brain activity; levels of brain chemicals including glutamate and GABA; white matter integrity; and neurocognition. We will collect whole brain data where possible and focus on the medial prefrontal cortex and parietal cortex as two regions of interest whenever whole-brain data collection is not possible due to technical limitations.

RESEARCH DESIGN AND METHODS

Enrollment: The study will enroll up to 30 healthy people with no history of psychiatric illness or family history of psychosis.

There are no restrictions on subject recruitment based on sex, ethnic background or health status other than those mentioned below. Individuals who do not speak English will be excluded.

Inclusion Criteria

1. Age: 21-50 years old.
2. Male or female.

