with HIPAA regulations and will store the information securely, protected by web authentication, and Secure Sockets Layer (SSL) encryption. Dietary information captured from the ASA24 is stored in an NIH-designed database that is completely deidentified. The only document linking the participant's username and study number will be kept in a password-protected computer file in a locked office at McLean.

Statistical Analysis: There is no published literature on the effects of olanzapine on the brain measures we plan to study. Therefore, it is not possible to calculate a sample size that would detect a given between-group difference in this study. In fact, our hypothesis is that olanzapine administration does not cause significant abnormalities in brain metabolism. Therefore, we plan to recruit a sample that is large enough to establish the absence of a moderate or large effect. Our proposed sample size of 30 subjects will allow us to detect a difference with effect sizes of 0.45 or greater as significant at the $p<0.05$ level with 80% power. Note that effect sizes of 0.5 are generally considered moderate and 0.8 considered large. Therefore, a non-statistically significant finding with our sample size will suggest that any effects of olanzapine on brain metabolism are at best small. We will examine deviations induced by the study drug on brain metabolism using paired t-tests for before and after measurements.

FORESEEABLE RISKS AND DISCOMFORTS

In terms of olanzapine treatment, the medication may be unsafe for some people and cause some unwanted side effects (*neurological, gastrointestinal, dermatological, ocular, musculoskeletal, hematologic, endocrine, metabolic, psychiatric*).

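### Effect size is stated only in SD units and a non-significant paired t-test is read as a small effect on brain metabolism, so noisy 31P measurement can favour the hypothesised null

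*Combined protocol and SAP*

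**What the plan says.** The Background section makes 31P MRS at 4 Tesla, before and after 15 days of olanzapine, the primary aim. The quantities of interest are levels of energy-related chemicals and "kinetics of enzymes involved in cellular energy metabolism in brains of healthy people before and after use of antipsychotic drug olanzapine". These are physical quantities with units.

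The Statistical Analysis paragraph under Research Design and Methods hypothesises no significant metabolic abnormality and aims to rule out effects of moderate or larger size. It states: "Our proposed sample size of 30 subjects will allow us to detect a difference with effect sizes of 0.45 or greater", "significant at the $p<0.05$ level with 80% power". It adds: "Note that effect sizes of 0.5 are generally considered moderate and 0.8 considered large". The analysis is done "using paired t-tests for before and after measurements". From a non-significant result it concludes that "any effects of olanzapine on brain metabolism are at best small".

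The documents do not give:
- the SD that standardises 0.45, or the sidedness of the test;
- any SD, CV or test-retest error for the 31P measures;
- a change in native units or percent that would matter;
- an equivalence margin or a confidence-interval rule.

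**The concern.** The conclusion is about brain chemistry, but the yardstick is a ratio. In a paired design the natural effect size is mean change divided by SD of change. That SD combines real differences between people in their response with the error of two scans. A small value can therefore mean little metabolic change or an imprecise spectrum, and the plan offers no means of telling them apart.

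The direction matters because no effect is the expected answer. With the true change held fixed, noisier data make non-significance more likely, and the plan reads non-significance as support for its hypothesis. The headline conclusion could then rest on measurement quality instead of biology.

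**Working it through.** **Inputs from the Statistical Analysis paragraph.** n = 30 pairs, alpha 0.05, 80% power, detectable effect size 0.45, paired t-test.

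**Assumptions (none are in the documents).** Effect size d = mean change / SD of change; SD of true change between people 5%; scan CV 5, 10, 15 or 20%; for the power row, a true mean change of 10%.

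**1. The plan's own figure.** By the normal approximation, detectable d = (z_alpha + z_power)/√n.
- One-sided 0.05: (1.645 + 0.842)/√30 = 0.454. Power at 0.45 is 79.4%, so the plan's figure is reproduced. The exact noncentral t gives d = 0.465 and power 77.7%.
- Two-sided 0.05: (1.960 + 0.842)/√30 = 0.511, with power 69.3% at 0.45. The exact noncentral t gives d = 0.529 and power 66.4%.

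If 0.45 is in SDs of change, it matches a one-sided test. A two-sided test matches only if 0.45 is in raw-score SDs with a before/after correlation of about 0.61 (normal) to 0.64 (exact t). The steps below use the exact two-sided value, 0.529.

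**2. How noise enters.** Two scans contribute error, so SD of change = √(5² + 2·CV²). The raw change detectable with 80% power is 0.529 × SD of change.

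| Scan CV (assumed) | 5% | 10% | 15% | 20% |
|---|---|---|---|---|
| SD of change | 8.7% | 15.0% | 21.8% | 28.7% |
| Change at d = 0.529 | 4.6% | 7.9% | 11.5% | 15.2% |
| d for a true 10% change | 1.15 | 0.67 | 0.46 | 0.35 |
| Two-sided power for that change | >99% | 94% | 68% | 45% |

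Example for CV 10%: √(25 + 200) = 15.0; 0.529 × 15.0 = 7.9; 10/15.0 = 0.67. The SD-scale limit is the same in every column, while the chemical change it stands for rises about threefold (15.2/4.6 = 3.3).

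**3. The same mechanism without percentages.** Take a fixed change equal to 0.80 noise-free SDs of change, and let noise add k times the true-change variance. Then d = 0.80/√(1 + k). For k = 0, 1, 2, 3, d = 0.80, 0.57, 0.46, 0.40, and the chance of a non-significant two-sided result is 1, 15, 31 and 44%.

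**4. What a null leaves open at any noise level.** The 95% CI half-width is t(0.975, 29)/√30 = 2.045/5.477 = 0.373 SD of change. A just non-significant result has an observed d of about 0.373, so its upper limit is 2 × 0.373 = 0.75 SD. That is above the plan's moderate benchmark and close to its large one.

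**The case against.** **The noise levels are assumed.** This stands. At a 5% scan CV, a 10% change is detected with more than 99% power and the problem is negligible. A reader might infer that 31P noise is high here, or that the plan concedes that precision data are lacking. Neither is supported. The plan says only that there is no published work on olanzapine's effects on these measures; on measurement reproducibility it is silent.

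**The plan does not grade an observed effect.** This also stands. The 0.45 is a detectability figure, 0.5 and 0.8 are glosses, and the decision rests on non-significance. A reader might infer that the benchmarks themselves move with noise. They are fixed numbers; it is their equivalent in chemical units that grows. Removing the benchmark labels alone would leave the faulty inference in place.

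**The standardiser is inferred.** True: with raw-score SDs the figures would differ. But the paired t-test itself scales by the SD of change, so scan error affects significance whichever SD was meant. A one-sided test does not remove this either: power for the 10% change is still 79% and 59% at CV 15% and 20%.

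**This is the missing equivalence test under another name.** Largely fair. Requiring the whole CI to lie inside a limit is an equivalence test. What this point adds is the scale: a 0.5 SD margin would also widen in chemical units as noise rises. The two matters should be handled together.

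**Conclusion.** The concern holds in limited form. Size is stated only in SD units, and non-significance is taken as evidence of a small effect. At n=30 that inference fails even without added noise, because a just non-significant two-sided result is compatible with effects up to about 0.75 SD of change. Measurement noise can add to this: under the assumed values, the change detectable with 80% two-sided power runs from 4.6% to 15.2% as scan CV goes from 5% to 20%.

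The 0.75 SD figure depends only on n=30 and a two-sided 95% interval. The percentages depend on the assumed SD of true change, the assumed CVs and d being scaled by the SD of change. They show sensitivity and do not estimate this study's precision. The documents support saying that noise can favour the null, not that it does. The change should be made because the affected sentence carries the study's main conclusion.

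**What to change.** In the Statistical Analysis paragraph:

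1. Replace the sentence that reads a non-significant result as showing a small effect.
2. For each 31P measure, report the mean change in native units or as percent change (a log ratio is optional), with its 95% CI and the SD of change.
3. Fix a limit in those units before the scans are processed. Conclude that the effect is at most small only if the whole CI lies inside it; otherwise report the result as inconclusive.
4. State the sidedness of the test and which SD the 0.45 refers to.

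Write this together with any change made for the absent equivalence test, so that there is one rule on one scale.

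The cost is SAP wording and the team's work in choosing and justifying a limit, for which the documents offer no basis. No extra data are needed. The downside is that, if the 31P data prove noisy, the study may have to report an inconclusive result.

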Participants will take daily olanzapine as the antipsychotic medication, Zyprexa Zydis. On the first day of medication each participant will take Zyprexa Zydis 2.5 mg/day PO. Dose will be increased in the second day and participants will be taking Zyprexa Zydis 5 mg/day, PO, for the following days.

The medication will always begin on weekdays except Friday. On the 1st and 2nd day of the medication, participants will be asked to take the medication at McLean Hospital. After they take the medication we will monitor them closely for 1 hour to observe any side effects.

If the participants do not have any unacceptable side effects in the first two days, then they will be able to take the 13 remaining doses at home starting from the third day

On the 2nd, 5th, and 10th days of medication we will administer LUNERS (Liverpool University Neuroleptic Side Effect Rating Scale), ESRS (Extrapyramidal Symptom Rating Scale) and the Columbia Suicide Severity Rating Scale to assess potential side effects better. Weight and vital signs assessment, random blood glucose test will be done and ECG will be taken in these visits. On 5th, 10th, and 14th days all participants will have blood drawn for assessment of olanzapine plasma levels. Each visit will take about 30 minutes to an hour.

Participants' dietary intake will be assessed throughout the study using the 24-Hour Food Recall ASA24 at visits 3 and 8, and with the Food Craving Questionnaire-Trait-reduced (FCQ-T-r) at the 1st, 7th and 9th visits.

We will still complete the study with participants who miss up to 3 days of medication administration and qualify those participants as having received the intended course of medication (while recording their degree of noncompliance). Participants who miss more than 3 days of medication will be discontinued from the study.

3. **Endpoint Assessments:** All participants will undergo final investigations on the 15th and 16th days of the medication follow up period. The participants will take their last olanzapine dose on the evening of the 15th day. They will not be asked to take it on the 16th day as we plan to finish all final assessments during daytime and they take their medications in the evening. Participants will undergo 4T MR scan and neurocognitive testing on the 16th day. All other assessment and 3T MR scans will be done on the 15th day. The third part of the study will consist of the following procedures:
 - a. Clinical evaluation (60 minutes)

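### A non-significant paired t-test is read as evidence that olanzapine's effects are small, yet 30 pairs miss a true moderate effect about 1 time in 4; an equivalence criterion should be stated in advance

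*Combined protocol and SAP*

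**What the plan says.** All the relevant text is in the combined protocol and SAP, mostly in the Statistical Analysis paragraph of Research Design and Methods.

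- **Purpose of the sample size.** The hypothesis is that olanzapine causes no significant abnormality, so "we plan to recruit a sample that is large enough to establish the absence of a moderate or large effect".
- **Power.** "Our proposed sample size of 30 subjects will allow us to detect a difference with effect sizes of 0.45 or greater", at p<0.05 with 80% power. Sidedness and the SD used to standardise the effect are not given.
- **Scale.** "Note that effect sizes of 0.5 are generally considered moderate and 0.8 considered large".
- **Test.** "We will examine deviations induced by the study drug on brain metabolism using paired t-tests for before and after measurements".
- **Conclusion drawn.** "a non-statistically significant finding with our sample size will suggest that any effects of olanzapine on brain metabolism are at best small".

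Two other places affect the number of pairs analysed. The Enrollment paragraph sets a ceiling: "The study will enroll up to 30 healthy people". The study-visits part foresees losses: "Participants who miss more than 3 days of medication will be discontinued from the study". No dropout allowance is stated. Nowhere do the documents give an equivalence margin or a rule based on a confidence interval.

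**The concern.** The trial expects a null result on its primary aim, and its only stated route to that conclusion is p not falling below 0.05. Failing to reject no-difference does not show that the difference is small. It can also come from too few pairs, noisy measurement or poor adherence.

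The 5% level protects against announcing an effect that is not there. The error that matters here is the opposite one: reporting effects as no more than small when a moderate effect exists. That error is limited only by power, which falls as participants are lost, so a weaker trial reaches the hypothesised conclusion more easily. At stake is the headline statement about a drug effect on the healthy brain.

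**Working it through.** **Inputs.** From the Statistical Analysis section: n = 30, level 0.05, power 80% at effect 0.45, moderate = 0.5, large = 0.8, paired t-test. Assumed because the plan is silent: two-sided test, effect d = mean change / SD of change. The two-sided assumption fits a hypothesis with no direction.

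**Formula.** The paired t statistic is noncentral t with df = n − 1 and noncentrality d√n. The miss rate is P(|T| < t_crit). For n = 30, t_crit = 2.045 (two-sided).

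**1. The plan's own figure (80% at 0.45).** Noncentrality = 0.45 × √30 = 2.46.

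- Two-sided: power 66.4%. The effect detectable with 80% power is 0.53.
- One-sided: power 77.7% (79.4% by normal approximation), close to the plan's figure.
- Two-sided with 0.45 in raw-SD units and an assumed before/after correlation of 0.64: d = 0.45 / √(2 × 0.36) = 0.53, power 80%.

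So the stated figure reproduces approximately one-sided, or two-sided with a correlation that the documents do not give.

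**2. Miss rates with 30 pairs.**

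| True effect d | Noncentrality | Two-sided | One-sided |
|---|---|---|---|
| 0.45 | 2.46 | 33.6% | 22.3% |
| 0.5 | 2.74 | 24.6% | 15.2% |
| 0.8 | 4.38 | 1.2% | 0.4% |

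**3. Fewer completers** (assumed numbers, two-sided, d = 0.5): 33% missed with 25, 35% with 24, 44% with 20.

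**4. A result just short of significance.** Observed d = 2.045 / √30 = 0.373. Inverting the noncentral t gives a 95% CI of 0.00 to 0.74 and a 90% CI of 0.06 to 0.68. The plan would call this small, while the interval runs past moderate and almost to large.

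**5. Equivalence criterion: noncentral-t 90% CI inside the margin, 30 pairs.**

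- Margin ±0.5: passes if |observed d| < 0.198. P(pass) is 71% at true 0, 65% at 0.1, 48% at 0.2 and 5% at 0.5.
- Margin ±0.8: passes if |observed d| < 0.486. P(pass) is 99% at true 0 and 5% at 0.8.
- Observed effects from 0.20 to 0.37 are non-significant while the 90% CI still includes 0.5. This happens in 24% of trials if the true effect is 0 (95.0% − 71.4% = 23.6%) and in 34% if it is 0.2.
- For 80% at ±0.5 with true 0: n = 35 gives 79.8%, n = 36 gives 81.2%. With n = 30, 80% is reached at a margin of about ±0.54.

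**6. Limit of an SD margin.** If noise doubles the SD of change, a raw effect worth 0.5 becomes 0.25. The t-test is then non-significant in 74% of trials and the ±0.5 criterion passes in 38%. A fixed raw margin equal to 0.5 of the original SD passes in 0.2%.

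**The case against.** The strongest objection is that the 1-in-4 figure depends on conventions the plan does not state and sits uneasily with its own power claim. If 80% power at 0.45 is taken as given, the miss rate at 0.5 is roughly 12% to 15%. In raw-SD units the two-sided miss rate at 0.5 depends on the before/after correlation: 39% at 0.3, 25% at 0.5, 12% at 0.64, 7% at 0.7 and 1.3% at 0.8 (all assumed correlations). This stands as a caution about the number. It does not rescue the inference. On the readings that match the plan, a moderate effect is still missed more than twice as often as the 5% an equivalence test allows, and only a high correlation near 0.8 removes the problem. A one-sided test also cannot support absence of change in both directions.

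Second, the plan says only that non-significance will suggest smallness, and its power statement does bound the error, nominally at 20% for 0.45. That is fair, but the stated purpose of the sample size is unhedged: "we plan to recruit a sample that is large enough to establish the absence of a moderate or large effect". No other rule governs the conclusion.

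Third, ±0.5, the 90% interval and the SD of change are choices the plan has not made. The margins come from the plan's own scale, and the minimum fix avoids these choices altogether.

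Fourth, this is a small mechanistic study and the CI could simply be given at reporting. True, but the faulty rule is attached to the primary aim and can be corrected now with a few lines.

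**Conclusion.** The concern holds and should be fixed before analysis. Non-significance with 30 pairs is reasonable evidence against a large effect (about 1% missed) but not against a moderate one. The miss rate at 0.5 is 25% under a two-sided 5% paired t-test with the effect in SD of change, and 15% if one-sided; it rises with every lost participant. The exact rate rests on those assumptions. The defect does not: a conclusion of absence is drawn with no margin and no interval, and the error of wrongly concluding absence is limited only by the power achieved.

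**What to change.** Replace the sentence quoted above on non-significant findings with:

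> For each brain-metabolism measure we will report the mean paired change in raw units with its 90% CI, and the standardised change (mean change / SD of change) with a noncentral-t 90% CI. We will claim absence of a moderate effect only if the standardised CI lies within ±0.5, and of a large effect only if it lies within ±0.8; otherwise the result is inconclusive.

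Keep the paired t-test for detecting a difference. State its sidedness and the standardiser, and give the power of the new criterion with 30 completers: for ±0.5, 71%, 65% and 48% at true changes of 0, 0.1 and 0.2; for ±0.8, 99% at 0. These are per measure; requiring absence on every measure cannot have higher power.

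Where a meaningful raw or percent change can be justified in advance, use it as the margin, because an SD margin does not protect against noisier scans. No margin cures poor adherence, so report the recorded non-compliance beside the result.

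**Cost.** Wording only; no new data or participants if this power is accepted. With a true effect of zero, the chance of claiming no moderate effect falls from 95% to 71%. Reaching 80% at ±0.5 would take 36 completers, above the ceiling of 30.

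**Minimum alternative.** Delete the sentence, report the CI, and state which effect sizes it does and does not exclude.

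### A single-arm paired t-test cannot show that a scan-to-scan change was caused by olanzapine, in either direction; the wording claims more than the design can deliver

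*Combined protocol and SAP*

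**What the plan says.** The design has one group. Under Study Visits: "Participants will take daily olanzapine as the antipsychotic medication, Zyprexa Zydis". The Background describes measurement "in brains of healthy people before and after use of antipsychotic drug olanzapine for 15 days", and Endpoint Assessments places the second scans on days 15 and 16. The placebo-controlled crossover described in the Medication paragraph is a cited earlier study, not this one.

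The Statistical Analysis paragraph names one method: "We will examine deviations induced by the study drug on brain metabolism using paired t-tests for before and after measurements". It states the hypothesis that olanzapine causes no significant abnormality, and it treats a non-significant result as support for effects that are small at most. The sample size claim is: "Our proposed sample size of 30 subjects will allow us to detect a difference with effect sizes of 0.45 or greater", at the 0.05 level with 80% power.

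Study Visits also provides: "On 5th, 10th, and 14th days all participants will have blood drawn for assessment of olanzapine plasma levels". On adherence it says: "We will still complete the study with participants who miss up to 3 days of medication administration", and the degree of noncompliance is recorded. Neither the levels nor the recorded noncompliance appears in any stated analysis.

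**The concern.** The mean of the paired differences is the drug effect plus every other systematic difference between a first and a second scan: scanner drift, familiarity with the scanner, or anything else that changes over about two weeks. With everyone treated, nothing in the paired test tells these apart, yet the plan attributes the whole change to the drug.

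The error can go either way. A non-drug shift can appear as a drug effect. A shift opposite to a real effect can cancel it and produce the null result that the plan expects. The second matters particularly here, because the plan intends to draw a substantive conclusion from non-significance.

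**Working it through.** **Inputs.** From the Statistical Analysis paragraph: n = 30, effect size 0.45, alpha 0.05, power 80%, paired t-test. From the Medication paragraph: olanzapine half-life 30 hours. Assumed, because the documents give no value: the size of any non-drug shift, the between-person coefficient of variation (CV) of plasma level, and that effect sizes are in units of the SD of change.

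**The plan's own figure.** The non-centrality is 0.45 × √30 = 2.465.
- One-sided normal approximation: Φ(2.465 − 1.645) = 79.4%, which matches the stated 80%.
- Two-sided: 69.3% by the normal approximation and 66.4% by exact t.

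Sidedness is not stated, which is a separate matter. The point here does not depend on it. The figures below are two-sided.

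**False attribution.** With no drug effect and a common non-drug shift of δ SD of change, the paired t statistic is non-central t with 29 df and non-centrality δ√30.

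| Assumed shift δ | δ√30 | Chance of p < 0.05 |
|---|---|---|
| 0 | 0 | 5.0% |
| 0.1 | 0.55 | 8.3% |
| 0.2 | 1.10 | 18.5% |
| 0.3 | 1.64 | 35.6% |
| 0.5 | 2.74 | 75.4% |

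**Masking.** A true effect of 0.5 SD with an opposite shift of 0.3 SD leaves a net 0.5 − 0.3 = 0.2 SD. Detection is then 18.5% if the effect is the same in everyone, and about 17-18% by simulation if it is proportional to plasma level. Without the opposing shift, a uniform 0.5 SD effect is detected in 75.4%.

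**What the plasma levels could add.** Simulation with 20,000 trials per setting, n = 30: level is lognormal with mean 1, and change = shift + effect × level + N(0, 1). The test is on the slope of change on level.
- With no drug effect and a shift common to all, the slope test rejects in about 5%, because a constant goes into the intercept.
- Power at assumed CVs of 30%, 50% and 70% is about 12%, 25% and 42% for a mean effect of 0.5 SD, and 34%, 69% and 87% for 1.0 SD.
- With an assumed level reliability of 0.7, the 0.5 SD figures fall to about 10%, 19% and 31%.
- With an assumed saturating response (half-maximum at 0.3 of the mean level), power is about 5-6%.
- If a participant trait linked to level moves the change by 0.3 SD per SD of log level (assumed) and the drug does nothing, the slope test rejects in about 30-33%.

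**Levels and missed doses.** Assume first-order elimination, instantaneous absorption and a sample just before that evening's dose. The fraction remaining after one day is k = 0.5^(24/30) = 0.574. Summing the scheduled doses (2.5 mg on day 1, then 5 mg) and dividing by the steady-state value 5k/(1 − k) gives 85%, 99% and 100% of steady state on days 5, 10 and 14. Missing day 13 alone puts the day-14 level at about 57% of steady state. Missing days 11 to 13, which the plan tolerates, puts it at about 19%.

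**The case against.** The strongest reply is that the regression does not repair the design. Attribution needs concurrent controls or untreated retest data, and a slope on observed levels supplies neither. That stands. Everyone has the same dose schedule, so levels differ through clearance and adherence, which are not randomised. A reader might infer that the slope is the one drug-specific contrast in the trial, or that its error rate holds at 5%. Neither is supported. Recorded missed doses also vary exposure, and the 5% holds only when level is unrelated to anything else that moves the scan. The 30-33% figure shows what happens otherwise.

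The power figures are also best case: a linear response, levels measured without error, and all 30 participants complete. The level summary is sensitive to recent missed doses. Leaving out day 5 is a preference, since a common factor of 0.85 would not bias a slope. The plan names no single primary 31P measure, so one slope per measure adds tests; with four independent tests the chance of at least one false positive is 1 − 0.95⁴ = 19%.

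Finally, the documents do not say why levels are drawn. They are listed with the side-effect visits, so not analysing them against imaging is a missed opportunity and not in itself an error. These objections limit the regression. They do not touch the wording: a single-arm paired change does not isolate a drug effect.

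**Conclusion.** The point holds as one about attribution. The plan calls a single-arm before-after change drug-induced and reads its absence as evidence that the drug does little. An assumed non-drug shift of 0.2-0.3 SD would raise the chance of a significant finding from 5% to about 19-36% with no drug effect. An opposing 0.3 SD shift would leave a true 0.5 SD effect detected in fewer than one trial in five.

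These shift sizes are illustrative. The documents contain no retest data, so one cannot conclude that such a shift exists or that the trial's result will be wrong. Nor can one conclude that using the plasma levels would close the gap: the exposure-response slope is exploratory, imprecise at n = 30 and open to confounding. The wording should change. The regression is an optional supplement.

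**What to change.** 1. In the Statistical Analysis paragraph, describe the result as *change over 15 days on olanzapine*. State that both a significant and a non-significant change may include non-drug shifts between scans. This costs only wording.

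2. As a supportive, exploratory analysis, pre-state a regression of the 31P change on one defined plasma-level summary, for example the mean of days 10 and 14. Name the 31P measure or measures in advance, take the recorded missed doses into account, and report the slope with its 95% CI. Say alongside it that:
   - the slope removes only shifts common to all participants;
   - levels are not randomised, so clearance or adherence can confound the slope;
   - power is low (about 12-42% for a mean effect of 0.5 SD at assumed level CVs of 30-70%, and lower with measurement error or a saturating response);
   - a null slope is not evidence of no effect.

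The regression uses data already collected and needs no new visit or procedure. Its downside is an imprecise extra estimate that does not replace a control group.
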